2.5 Pulmonary Function (PaO2/FiO2) (in a subset of patients)

 PaO_2/F_iO_2 up to and incl. Day 7 will be evaluated as an area under the curve (AUC). Linear interpolation will be used to derive the AUC (taking into account that not all patients will have measurements taken between 24 hours post baseline and Day 2). Patients dead or withdrawn will be set to missing. The cumulative PaO_2/F_iO_2 will be compared between treatment arms using a repeated measures ANCOVA model with baseline PaO_2/F_iO_2 as covariate, treatment, time and treatment by time interaction as factors, baseline PaO_2/F_iO_2 by time interaction, and patient as the experimental unit. Estimated treatment differences (to placebo) along with a 95% confidence interval will be presented.

2.6 Arterial Blood Gases and Acid/Base Status (PaO2, PaCO2, pH, SaO2, Bicarbonate, Base Excess), Lactate and Oxygen Saturation in Vena Cava Superior (ScvO2)

Lactate up to and incl. Day 7 will be evaluated as for PaO₂/F_iO₂ in section 2.5 above.

2.7 Time to Out of Shock

A Kaplan-Meier analysis will be performed for time to out of shock, defined as the first time where the patient has no vasopressor for at least 24 hours. Patients who die or are withdrawn while still on vasopressors and before first 24 hour vasopressor-free episode will be censored. The same applies for patients prematurely discontinued from IMP.

Page 8 of 9

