3.2 Determination of Sample Size

At least 1800 evaluable patients combined for Part 1 and Part 2 are needed for the final analysis. The overall power of obtaining statistical significance based on combined evidence from Part 1 and Part 2 is 91% in situations where all 4 arms have a true underlying 1.5% lower mortality rate and a 1.5-day higher expected number of P&VFDs for survivors as compared to placebo (corresponding to an overall treatment effect of 1.5 P&VFDs). If the effect sizes are 2% on mortality and 2 days for P&VFDs in survivors for all 4 arms (corresponding to an overall treatment effect of 2 P&VFDs), then the overall power is 98%. In this latter case the probability of engaging into Part 2 is ~99%.

Date: 20 Nov 2017 E-Statistical Analysis Plan-17877; Ver.9.0 Supersedes: Ver. 8.0

Page 18 of 80

4 Patient Disposition

A summary table will present, for each part of the trial and overall, the number of patients in the population sets: 'Screened', 'Intention to treat', Full analysis set', 'Per protocol', 'Safety', 'Completed trial', 'Withdrawals', and 'IMP discontinuations' with a breakdown of reasons/categories for trial withdrawals and IMP discontinuations.

The patient disposition table will be broken down by each of the stratification variables [the need for mechanical ventilation (Yes/No), norepinephrine/noradrenaline requirement at baseline (< or \ge 30 µg/min) and creatinine (< or \ge 150 µmol/L)] and broken down chronologically displaying number of patients 'completed' and 'withdrawn from trial' at Day 30, Day 90 and Day 180.

The number of patients screened but not randomised/allocated to treatment will be presented with the reason(s) for screen failure in a data listing.

All major protocol violations (including misrandomisations), based on the Full analysis set, will be summarised for each part of the trial.

Furthermore 1-KM plots, based on the ITT, will be presented for the time to trial withdrawals/IMP discontinuations (whichever comes first) differentiated by reason of trial withdrawal/IMP discontinuation using cumulative incidence functions. Dropout rates between treatment groups will be evaluated by the log-rank test.

Date: 20 Nov 2017 E-Statistical Analysis Plan-17877; Ver.9.0

Supersedes: Ver. 8.0 Page 19 of 80

5 Protocol Deviations

Patient data in the full analysis set (FAS) will be excluded from the per-protocol (PP) analysis set if they meet any of the following criteria:

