9.2 Primary Endpoint

• Vasopressor- and mechanical ventilator-free days (P&VFDs) up to day 30

This composite endpoint is defined as the number of days (reported to one decimal place (0.0 to 30.0)) from start of treatment with the investigational medicinal product (IMP) [selepressin or placebo] to 30.0 days thereafter during which the patient is: 1) alive; 2) free of treatment with intravenous vasopressors; and 3) free of any invasive mechanical ventilation (see definition below).

Patient Death

By definition, any patient that dies within this 30-day period will be assigned zero P&VFDs, even if there is a period during which the patient is alive and free of both vasopressor treatment and mechanical ventilation.

Definition of "Free of Vasopressors"

Free of vasopressors means less than 60 minutes during any contiguous 24-hour period (regardless of calendar day). If a patient requires periods of vasopressors longer than 60 minutes in total during any 24-hour period, the intervening intervals during which they are free of vasopressors will not be included in the period free of vasopressors in the determination of the number of P&VFDs. Thus, the period free of vasopressors begins at the end of the last use of vasopressors that was either: 1) longer than 60 minutes in duration; or 2) part of greater than 60 minutes of use within a contiguous 24-hour period.

Norepinephrine/noradrenaline, phenylephrine, dopamine, epinephrine/adrenaline, vasopressin, terlipressin, and IMP (i.e. selepressin and placebo) all constitute a vasopressor for the purpose of the primary analysis.

Vasopressor use due to anaesthesia or procedure-induced hypotension during and up to three hours after a surgery or procedure (including bedside) is exempt from this rule (i.e. such use of vasopressors would not affect the calculation of P&VFDs).

Date: 20 Nov 2017 E-Statistical Analysis Plan-17877; Ver.9.0 Supersedes: Ver. 8.0

Page 24 of 80

Definition of "Free of Mechanical Ventilation"

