Some patients will get out of shock prior to Day 30 (and stay alive until Day 30), some will get out of shock and die later on (prior to Day 30), others will die or be withdrawn while still in shock (prior to Day 30), and the remaining few will not get out of shock prior to Day 30. This means that if mortality and withdrawal rates vary between treatment arms, the results of the analysis for the overall population will be influenced by the skewed mortality and withdrawal rates. Hence, for the overall population, the distribution of duration of shock (time to out of shock), will be presented graphically as competing risks between 'time to out of shock', 'withdrawn while in shock' and 'dying while in shock'. Further, Kaplan-Meier (sub)-graphs on 'time to death' and 'time to withdrawal' will be presented for those getting out of shock (for which some will die or be withdrawn later on, prior to Day 30). This is done in order to elucidate any skewness in mortality and withdrawal rates, influencing the results of the analysis.

Furthermore, duration of septic shock will be tabulated by treatment arm (including pooled active treatment arms).

In case the model assumptions does not hold, covariates will be dichotomised (in same manner as they have been dichotomised for other endpoint analyses) and duration of septic shock will be analysed using a stratified permutation test (Monte Carlo estimate of p-value). Treatment effects (and treatment difference) will be the raw (unadjusted/non-stratified) means. The confidence intervals for the individual treatment arms will be derived by bootstrapping 5000 samples (within treatment group) with same number of observations (within treatment group), and taking the 2.5 and 97.5% percentiles from the distribution of the 5000 means from the bootstrapped samples. The confidence interval for the treatment difference will be derived via significance testing (based on the stratified permutation test), i.e. the confidence interval will be constructed by including the 95% confidence region for all those values for which the significance test of the hypothesis that the true value is the given value is not rejected at a 5% significance level (e.g. if we test is treatment difference=1 and p-value >0.05 then we include 1 in the confidence interval, and so on). The seed for both the Monte Carlo derived p-value and the bootstrapped confidence intervals will (appropriately) be seed=133.

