Duration of RRT will be analyzed as for duration of ventilation (also by transforming to integers) in Section 9.3.1.4 with time from onset of shock to start of treatment, baseline creatinine and norepinephrine/noradrenaline requirement at baseline (μ g/kg/min) as covariates, and treatment and need for ventilation as factors. The supportive competing risk and Kaplan-Meier graphs described in Section 9.3.1.4 will not be performed as it makes no sense since RRT durations are short and repetitive. It is more meaningful to just look at 90 day mortality and withdrawal rates to take eventual skewed mortality and withdrawal rates into account.

Page 35 of 80

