This document describes the statistical analyses for selepressin (FE202158) 000133 planned after the trial was stopped for futility, but before the blind was broken. It is an addendum to version 9.0 of the statistical analysis plan.

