2.8 Time to Out of Mechanical Ventilation

Time to out of mechanical ventilation will be defined and analyzed similarly as for time to out of shock in section 2.7 above.

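### Addendum 2.7 and 2.8 censor deaths on vasopressors or ventilation in a Kaplan-Meier analysis, so 1-KM overstates recovery and can hide or reverse the effect of excess deaths

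*SAP*

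**What the plan says.** Addendum 2.7 defines time to out of shock as the time to the first period of at least 24 hours without any vasopressor and analyses it by Kaplan-Meier. On censoring it says: "Patients who die or are withdrawn while still on vasopressors and before first 24 hour vasopressor-free episode will be censored". It then adds: "The same applies for patients prematurely discontinued from IMP". Addendum 2.8 extends this to ventilation: "Time to out of mechanical ventilation will be defined and analyzed similarly as for time to out of shock". Neither section mentions competing risks, names a between-arm test, or says what quantity the curve is meant to estimate.

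The main SAP handles a closely related question differently. Section 9.3.1.3 warns that unequal mortality or withdrawal will distort the overall duration-of-shock result. The distribution of time to out of shock therefore "will be presented graphically as competing risks between 'time to out of shock', 'withdrawn while in shock' and 'dying while in shock".

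For ventilation the position is less clear. Section 9.3.1.9, on RRT, says: "The supportive competing risk and Kaplan-Meier graphs described in Section 9.3.1.4 will not be performed". The text of 9.3.1.4 describes no such graphs.

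The addendum's introduction states its relation to the main plan: "It is an addendum to version 9.0 of the statistical analysis plan". The graphs in 9.3.1.3 therefore remain planned.

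**The concern.** Kaplan-Meier censoring assumes that a censored patient has the same future chance of the event as those still at risk. A patient who dies on vasopressors has none. The estimator in effect passes that patient's weight to those still at risk, so the curve climbs towards 100% however many die. It does not estimate the share of randomised and dosed patients who get out of shock or come off the ventilator, yet a reader will naturally take it that way.

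The comparison between arms is also at risk. If one arm has more deaths in shock, its curve need not show it. If those deaths fall mainly on patients who would have recovered slowly, that arm's curve moves upwards.

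Censoring at premature IMP discontinuation is a second, separate source of informative censoring. It discards vasopressor and ventilator records that the primary endpoint needs anyway, because SAP 9.2 counts days from start of IMP "to 30.0 days thereafter during which the patient is: 1) alive; 2) free of treatment with intravenous vasopressors". SAP section 4 also treats stopping IMP as distinct from leaving the trial, "with a breakdown of reasons/categories for trial withdrawals and IMP discontinuations".

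**Working it through.** The plan gives no figure for these analyses, so there is nothing to reproduce. The check compares 1-KM (deaths censored) with the true cumulative incidence of recovery.

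**Inputs**
- Mean time to recovery of 5-8 days: SAP Appendix 3, expected time on vasopressors and ventilation in survivors. It is a proxy, because it combines both supports. A mean of 3 days is added as an assumed shorter case for shock.
- Share dying in the state by Day 30: not given, so assumed at 10%, 15% and 25%. Appendix 8 assumes 25% placebo mortality, which includes deaths after leaving the state.
- Horizon of 30 days, as in SAP 9.3.1.3.

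**1. Size of the overstatement (constant hazards)**

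With recovery hazard l1 = 1/mean and death hazard l2:
- 1-KM(t) = 1 - exp(-l1 t)
- true recovery(t) = l1/(l1+l2) × [1 - exp(-(l1+l2)t)]
- l2 is solved so that l2/(l1+l2) × [1 - exp(-30(l1+l2))] equals the assumed share dying.

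Day 30, with 15% dying in the state:

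| Mean to recovery | 1-KM | True |
|---|---|---|
| 3 days | 100% | 85.0% |
| 5 days | 99.8% | 84.9% |
| 8 days | 1 - exp(-3.75) = 97.6% | 83.8% |

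Over all cases (3-8 days, 10-25% dying) the Day 30 excess is 9.2 to 25.0 points, roughly the share who die. At Day 7, with means of 5-8 days, it is 2.4 to 11.9 points.

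A cross-check takes 5-8 days as the mean time to leave the state by either route. The Day 30 excess is then 8.9 to 24.1 points.

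**2. Effect on an arm difference (two classes, all values assumed)**

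30% recover slowly (recovery hazard 1/12 per day, death 0.05) and 70% quickly (recovery 1/2, death 0.005). The hazard that Kaplan-Meier sees is the average recovery hazard among those still at risk. Numerical integration gives:

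| Scenario | Deaths in state, Day 30 | True recovery, Day 30 | 1-KM, Day 7 | 1-KM, Day 30 |
|---|---|---|---|---|
| Baseline | 11.7% | 87.7% | 82.7% | 97.9% |
| (a) Death +0.03 per day in everyone | 19.2% | 80.6% | 82.7% | 97.9% |
| (b) Slow-class death 0.05 to 0.06 | 13.1% | 86.5% | 83.0% | 97.9% |
| (c) Slow-class death 0.05 to 0.12 | 18.4% | 81.6% | 85.1% | 98.4% |

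In (a) a 7.1-point loss of recovery (87.7 - 80.6) is invisible. In (c) a 6.1-point loss (87.7 - 81.6) appears as a gain.

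A second set of assumed hazards gives the same pattern: 30% severe, recovery 0.05 against 0.30, death 0.06 against 0.01. Doubling the severe-class death hazard lowers true Day 30 recovery from 80.9% to 76.5%, while 1-KM rises from 95.0% to 97.2%.

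**3. IMP discontinuation alone**

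In the first two-class model, set deaths to zero and censor 0.10 per day in one class only. The true Day 7 recovery is 81.1%. Kaplan-Meier gives 84.6% if only slow recoverers stop IMP and 77.8% if only fast recoverers do. The direction depends on who stops.

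**The case against.** The strongest reply is that the whole package does not hide deaths. The competing-risk display in 9.3.1.3 stays in force, mortality has its own analysis and Kaplan-Meier plot (9.3.2.3), and the durations of shock and ventilation are also analysed separately for survivors and non-survivors. For ventilation, the cross-reference in 9.3.1.9 and the change log for version 7, which mentions competing-risk graphs for the remaining duration endpoints, suggest that such graphs are intended and that 9.3.1.4 merely omits them. A death-censored curve can also be read as a description of the cause-specific recovery hazard, shown beside a cumulative incidence plot. Censoring at IMP discontinuation might reflect an on-treatment question.

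Much of this stands as a limit on importance. It does not repair the curve. The 9.3.1.3 display uses a different event, since 2.7 counts the first 24 vasopressor-free hours, and the addendum does not refer to it. The ventilation graphs are not specified where the plan says they are. Neither 2.7 nor 2.8 declares a cause-specific or on-treatment target.

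It is also fair that the reversal depends on assumed hazards and can be small: in scenario (b) it is 0.3 points at Day 7 and nil, to one decimal, at Day 30. That supports saying the effect can reverse, not that it will.

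**Conclusion.** The concern holds. As written, 1-KM from 2.7 and 2.8 is not the proportion out of shock or off ventilation. By Day 30 it exceeds that proportion by about the share who die in the state: 9.2 to 25.0 points under the assumed 10-25% and means of 3-8 days. That it overstates recovery follows from the method whenever deaths precede recovery; only the size rests on assumptions. Masking of excess deaths needs no more than equal recovery hazards with unequal death hazards. Reversal needs the excess to fall on slow recoverers.

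The consequence is confined to supportive analyses planned after the futility stop and before unblinding. The primary test scores deaths as zero P&VFDs and is untouched, as are the key secondary claims. The change should be made, but the trial's main conclusion does not depend on it.

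**What to change.** In 2.7 and 2.8, replace Kaplan-Meier with the Aalen-Johansen cumulative incidence of the first 24 hours free of vasopressor (or ventilation), with death in that state as a competing event. Holding such deaths as never recovered to Day 30 gives the same answer when nobody is censored earlier. It is only approximate if withdrawals are censored, which should matter little because SAP 9.3.4.1 expects fewer than 20 withdrawals before Day 7.

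State how withdrawal is handled: either as a separate category, as in 9.3.1.3, or as censoring at trial withdrawal only. Do not censor at IMP discontinuation; use the vasopressor and ventilator records to Day 30. If the arms are to be compared formally, use a test that matches the cumulative incidence, such as Gray's test.

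The cost is two or three sentences in the addendum, standard software and no new data. The reported recovery proportions will be lower than the Kaplan-Meier version would show.

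### Addendum 2.7, and 2.8 on its natural reading, censor patients at premature IMP discontinuation although the SAP's 30-day endpoints imply that their vasopressor and ventilator status is still observed

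*SAP*

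**What the plan says.** Addendum 2.7 sets out the method and event: "A Kaplan-Meier analysis will be performed for time to out of shock, defined as the first time where the patient has no vasopressor", with a minimum vasopressor-free gap of 24 hours. Two censoring rules follow. The first is "Patients who die or are withdrawn while still on vasopressors and before first 24 hour vasopressor-free episode will be censored". The second is "The same applies for patients prematurely discontinued from IMP". The time of censoring is not spelled out; the natural reading is the time IMP is stopped. No reason is given, 'prematurely' is not defined in the addendum, and the addendum plans no version without the rule.

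Addendum 2.8 reads "Time to out of mechanical ventilation will be defined and analyzed similarly as for time to out of shock in section 2.7 above". It does not repeat the censoring rules, but the natural reading is that they apply.

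The main SAP handles the same data differently:

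- Section 9.2 counts vasopressor- and ventilator-free time "from start of treatment with the investigational medicinal product (IMP) [selepressin or placebo] to 30.0 days thereafter". Other vasopressors count as well as IMP, and the imputation rules address missing data, not an IMP stop.
- Sections 9.3.1.3 and 9.3.1.4 measure shock and ventilation from IMP start to Day 30 and truncate only at withdrawal or death.
- Section 9.3.1.3 plans a display of time to out of shock "presented graphically as competing risks between 'time to out of shock', 'withdrawn while in shock' and 'dying while in shock". An IMP stop is not one of the exits.
- Section 4 lists trial withdrawals and IMP discontinuations as separate categories.

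**The concern.** Kaplan-Meier gives a censored patient the later recovery rate of those still at risk. That is a fair device when the later course is unknown. Here it seems to be known, and patients taken off IMP early while still needing a vasopressor may well not share the outlook of those who continue.

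Stopping may also differ between a vasoactive drug and placebo. If it does, the curves no longer compare the randomised arms on all their follow-up. An arm with more stops followed by long shock on other vasopressors would show no penalty. Conversely, an arm with faster recovery on IMP but more stops could show an advantage that full follow-up would not. Either result could disagree with P&VFDs and with the Section 9.3.1.3 analyses on the same patients.

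For ventilation the link between IMP and outcome is looser still. If the rule carries over, a ventilated patient whose IMP stops prematurely on Day 1 contributes nothing afterwards, although ventilator time is counted to Day 30.

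**Working it through.** **Is the outcome observed after an IMP stop?** No single sentence says so. It follows from Section 9.2 (30.0 days from IMP start, with no condition on staying on IMP), Sections 9.3.1.3 and 9.3.1.4 (cut only at withdrawal or death) and Section 4 (IMP discontinuation separate from withdrawal). The change log entry for version 6 adds that an adverse event is not a ground for withdrawal from the trial, while Section 10.2.1 tabulates adverse events leading to IMP discontinuation. Section 10.2 still mentions narratives for adverse events leading to withdrawal, so the change log entry is support rather than proof. P&VFDs could not be derived as Section 9.2 describes without this follow-up.

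**How much can it matter?** The SAP gives no rate for this analysis, so there is no planned figure to reproduce. All inputs below are assumed:

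- no deaths;
- recovery rate on IMP h = 1/3 per day (mean 3 days);
- a fraction f of patients subject to an early stop at rate c = 1 per day, effective only if still in shock;
- recovery rate r·h after the stop.

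The share stopped in shock is f·c/(c + h) = 0.75f. So f = 10%, 20%, 25% gives 7.5%, 15%, 18.75% (about 19%).

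The planned curve at Day 7 is 1 − exp(−7/3) = 1 − 0.0970 = 90.3%, whatever f and r are.

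Among patients subject to a stop, the proportion still in shock at t = 7 is

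A(r) = exp(−(h+c)t) + c[exp(−rht) − exp(−(h+c)t)]/(h + c − rh).

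The all-follow-up proportion out of shock is 1 − (1 − f)(0.0970) − f·A(r).

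| Recovery after stop, r | A(r) | 7.5% stopped | 15% stopped | 19% stopped | Planned curve |
|---|---|---|---|---|---|
| 2 | 0.0141 | 91.1% | 92.0% | 92.4% | 90.3% |
| 1 | 0.0970 | 90.3% | 90.3% | 90.3% | 90.3% |
| 1/2 | 0.2669 | 88.6% | 86.9% | 86.1% | 90.3% |
| 1/3 | 0.3759 | 87.5% | 84.7% | 83.3% | 90.3% |
| 0 | 0.7500 | 83.8% | 77.2% | 74.0% | 90.3% |

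For example, r = 1/3 and f = 20%: 1 − 0.8 × 0.0970 − 0.2 × 0.3759 = 84.7%.

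**Between arms.** Take 15% stopped in one arm and 7.5% in the other, with equal recovery on IMP. The planned curves coincide. The all-follow-up difference at Day 7 is +0.8 points at r = 2, 0 at r = 1, −1.7 at r = 1/2, −2.8 at r = 1/3 and −6.5 at r = 0.

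**A second model as a check.** Let every patient in shock face a constant stop rate, with h = 0.35 per day. The curve then shows 1 − exp(−2.45) = 91.4%. With 5% stopped in shock, all follow-up gives 90.3%, 89.4% and 87.8% for r = 1/2, 1/4 and 0. With 20% stopped it gives 87.1%, 82.9% and 76.3%. The overstatement runs from about 1 to 15 points and is zero at r = 1. A simulation of 400,000 patients (20% stopped, r = 1/4) gave 91.4% on the curve against 83.0% with all follow-up.

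**The case against.** The best defence is that little rests on these curves. They were added after the futility stop and before unblinding, and 2.7 names no test or success criterion. For shock, Section 9.3.1.3 already plans a competing-risk display that does not exit patients at an IMP stop. Section 4 plans cumulative incidence plots of withdrawal or IMP discontinuation by reason, with a log-rank test, so an imbalance in stopping would be seen. The addendum also seeks on-drug views elsewhere (2.1, near-perfect conditions of use; 2.9, target MAP while on IMP), and a curve censored at IMP stop is a recognised, if assumption-heavy, view of that kind. All of this stands and limits the severity. It does not remove the point: 2.7 does not label its curve as an on-treatment view, and Section 4 shows the stopping but not its effect on the curve. For ventilation the cover is thinner, since Section 9.3.1.9 refers to such graphs in Section 9.3.1.4 but the text there does not describe them.

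A reader might go further in three ways that the documents do not support:

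- **That those censored are patients in whom treatment failed.** Adverse events leading to IMP discontinuation are tabulated, but treatment failure is not listed as a reason for stopping, and the definition of premature stopping may lie in the protocol.
- **That the curve must be too favourable.** The direction depends on recovery after the stop. Slower recovery is more plausible for patients stopped in shock, but faster recovery reverses the bias and nothing in the SAP excludes it.
- **That the trial's conclusion is affected.** The primary and key secondary tests do not use this rule.

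**Conclusion.** The point holds, at minor severity. Addendum 2.7, and 2.8 on its natural reading, set aside follow-up that the main SAP uses, under a censoring assumption that is probably informative. In the illustration the Day-7 proportion is understated by up to about 2 points if recovery doubles after the stop, unaffected if it is unchanged, overstated by about 2 to 4 points at half the rate and 3 to 7 points at one third, and by up to 16 points with no later recovery. Unequal stopping can hide or create a difference between arms. These sizes rest on assumed rates and no deaths. That data continue after an IMP stop is an inference from the endpoint definitions, though a strong one.

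**What to change.** In Addendum 2.7, delete "The same applies for patients prematurely discontinued from IMP" and state that patients who stop IMP are followed to the event, death, trial withdrawal or Day 30. State in 2.8 that the same holds for ventilation.

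Deleting the sentence alone would leave deaths censored in the same curve, whereas Section 9.3.1.3 treats death in shock as a competing event. Replace the Kaplan-Meier estimate in both sections with cumulative incidence, with death as a competing event.

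If an on-IMP view is wanted, keep the curve censored at IMP stop as a sensitivity analysis labelled on-treatment, with its assumption stated.

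The cost is a few lines in the addendum and, if the on-IMP view is kept, one extra curve per endpoint. The data needed are those already used for P&VFDs.
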